1.3 RATIONALE FOR PERFORMING THE TRIAL

This trial is an extension trial of the 1199.247 parent trial, INBUILD®. All patients still receiving blinded treatment at the end of part B of the parent trial had the possibility to receive open label nintedanib in this extension trial.

The aim of this extension trial is to evaluate long term tolerability and safety of nintedanib in patients with PF-ILD.

1.4 BENEFIT - RISK ASSESSMENT

In the group of patients with PF-ILD the natural history of the disease appears to follow a course similar to IPF with worsening of respiratory symptoms, lung function, quality of life (QoL) and functional status, as well as early mortality. With the exception of nintedanib and pirfenidone, which were available for patients with IPF, there was no approved therapy for PF-ILD at the start of this trial.

Based on the efficacy and safety shown in IPF patients, and considering the similarity of the pharmacological rationale between IPF and PF-ILD, the same dose regimen of 150 mg nintedanib bid is considered appropriate.

This extension trial only started recruiting when the results from the initial database lock (i.e. the efficacy and safety results after 52 weeks of treatment) of the INBUILD® trial had been reviewed and justified the start of this extension study. This meant that the nintedanib-treated patients showed a lesser decline in lung function compared to the placebo-treated group, and that the safety and tolerability was acceptable with no new relevant safety issues identified that influenced the existing benefit-risk assessment. The first day of this extension trial was on the same day as the last visit of the parent trial to allow continuous treatment.

All patients receive active treatment in this trial.

The risks of treatment with nintedanib have been well delineated in patients with the fibrotic lung disease IPF. These risks are primarily related to the gastrointestinal tract (diarrhoea, nausea, vomiting, abdominal pain), and are usually managed with supportive therapy and with temporary or permanent dose reduction to 100 mg bid. In some cases, temporary interruption or permanent drug discontinuation is necessary. A reduction in appetite and weight decrease has also been reported in patients treated with nintedanib.

The potential for drug-induced liver injury (DILI) is under constant surveillance by sponsors and regulators. Cases of drug-induced liver injury (DILI) have been observed with nintedanib treatment. The majority of patients presented with mild to moderate liver enzyme elevation, which was in most cases transient upon dose reduction or treatment discontinuation. However, severe DILI with fatal outcome has also been reported. Therefore, this trial requires timely detection, evaluation, and follow-up of laboratory alterations in selected liver laboratory parameters to ensure patients' safety. Nintedanib must be dose-reduced, or interrupted in the event of hepatic toxicity and further treatment withheld until recovery of the abnormal laboratory parameters (see also section [4.2.1.2](#) and [5.2.5.1.4](#)).

Concomitant therapies with a known overlap in side effects with nintedanib (e.g. gastrointestinal [GI] adverse events, increase of AST, ALT, bilirubin) or concomitant use of therapies that interact with metabolism of nintedanib (through UGT1A1 and P-gp) should be used with caution and patients should be closely monitored (see section [4.2.2.2](#)).

Potential risks of nintedanib treatment also include gastrointestinal perforations and thromboembolism. Hypertension, thrombocytopenia and bleeding are considered side effects of nintedanib treatment in IPF. Therefore, the use of full dose therapeutic anticoagulation, fibrinolysis or high-dose antiplatelet therapy is not recommended during the trial, and patients requiring such a treatment should only be treated with nintedanib if the anticipated benefit outweighs the potential risks.

The mode of action of nintedanib indicates a high potential for teratogenicity and embryotoxicity, including fetotoxicity and lethality. In women of childbearing potential receiving nintedanib, contraceptive measures must be employed 28 days before treatment initiation, during the treatment and for a period of 3 months after last drug intake.

The underlying diseases should be managed in accordance with current standard management practices. In some of the underlying diseases, immunosuppressive agents as well as of non-immunosuppressive therapies are commonly used to treat organ-specific manifestations, and need to be considered although appropriate randomised-controlled data for these therapies are lacking. Cautionary notes are included in the protocol (section [4.2.2.2](#)) with regard to such therapies whose safety profile could interfere with that of nintedanib.

Safety will be closely monitored at site visits, including physical examinations, safety laboratory and specific monitoring procedures, to follow-up potential hepatic enzyme elevation and exclusion of pregnancy. In addition, safety laboratory results will be monitored at intermediate lab visits in the first year. In patients who develop severe symptoms of gastrointestinal toxicity not amenable to symptomatic treatment with standard measures or severe liver enzyme elevations or other severe adverse events as specified in section [3.3.4](#), treatment with nintedanib must be discontinued and appropriate therapeutic measures taken.

Based on the pharmacological mechanism, existing non-clinical, clinical and post-marketing data there is no indication that treatment with nintedanib may increase the risk for infection with SARS-CoV-2 or for worsening the disease course of COVID-19. It is currently unknown whether PF-ILD conveys a higher risk for adverse outcomes in case of COVID-19.

The trial related risk to the COVID-19 pandemic situation is the general risk of travelling to site and being at site for assessments with increased infection risk for lung function testing. Risk mitigation and possible modifications are described in Section [6.1](#) and in Appendix [10.3](#)

In conclusion, the benefit-risk profile is considered appropriate for this stage of clinical development.

2. TRIAL OBJECTIVES AND ENDPOINTS

2.1 MAIN OBJECTIVES, PRIMARY AND SECONDARY ENDPOINTS

2.1.1 Main objectives

The main objective is to assess long term tolerability and safety of treatment with oral nintedanib in patients with Progressive Fibrosing Interstitial Lung Disease (PF-ILD) who have completed (and did not prematurely discontinue trial medication in) the phase III parent trial, INBUILD® (trial 1199.247).

2.1.2 Primary endpoint(s)

The primary endpoint is the incidence of overall adverse events over the course of this extension trial.

2.1.3 Secondary endpoint(s)

No secondary efficacy endpoints are defined.

3. DESCRIPTION OF DESIGN AND TRIAL POPULATION

3.1 OVERALL TRIAL DESIGN AND PLAN

This is a multi-centre, multi-national, prospective, open label extension clinical trial. It is estimated that approximately 480 patients with PF-ILD will complete the INBUILD® trial 1199.247 (part A and part B) on blinded treatment. These patients will be eligible for enrolment in this extension trial. Patients who withdrew treatment prematurely in the INBUILD® trial will not be eligible for the open label extension trial (INBUILD®-ON).

At the time point when the data from the INBUILD® trial for patients with PF-ILD are available, and justify the start of the extension trial, all patients on blinded treatment at the end of the parent trial can be offered participation in the current rollover study.

After signing Informed Consent, and if all eligibility criteria are met, patients will initiate treatment with nintedanib (Visit 1) (refer to section [4.1.3](#)). Patients will receive active drug at a dose of 150 mg bid or 100 mg bid, depending on their last dose of blinded medication in the parent trial. Patients whose last dose of blinded medication in the parent trial was 150 mg bid will receive nintedanib 150 mg bid in the extension trial. Patients who dose reduced to 100mg bid in the parent trial, can either receive nintedanib 100 mg bid or be offered nintedanib at the dose of 150 mg bid based on the judgement of the investigator.

In order to collect long-term safety data in patients with PF-ILD, all patients will be requested to stay in the trial for 96 weeks (until visit 12). At week 96, patients who can be treated with nintedanib outside the clinical trial will have their EOT visit. The remaining patients will continue in the trial until nintedanib can be made available to them outside the clinical trial. Treatment will be stopped if a reason for withdrawal is met (refer to section [3.3.4](#)). Overall, the trial is estimated to last a total of approximately 36 months.

3.2 DISCUSSION OF TRIAL DESIGN, INCLUDING THE CHOICE OF CONTROL GROUP(S)

The trial will be conducted as a prospective, open-label trial. This design is appropriate for assessing the long-term tolerability and safety of nintedanib in patients with PF-ILD.

All patients eligible for this extension study will have completed the parent trial, i.e. were treated with blinded study drug (nintedanib or placebo) for at least 52 weeks and did not prematurely discontinue blinded treatment. All patients in the extension study will receive active treatment as prolonged use of placebo would not be appropriate.

3.3 SELECTION OF TRIAL POPULATION

It is anticipated that approximately 480 patients, from approximately 160 sites in about 15 countries, will complete the INBUILD® trial and will consent to participate (and thus receive treatment) in this extension trial. At the start of the open label extension trial it is not known which treatment the patients have received in INBUILD®. Patients previously on active treatment will continue treatment with nintedanib, patients who received placebo will initiate treatment with nintedanib for the first time at Visit 1 of the extension trial.

A log of all patients enrolled into the trial (i.e. who have signed informed consent) will be maintained in the Investigator Site File (ISF).

If a patient is entered in error (does not meet all inclusion criteria or meets one or more exclusion criteria on the day of enrolment), the sponsor should be contacted immediately.

3.3.1 Main diagnosis for trial entry

Only patients with PF-ILD who have completed the parent trial (INBUILD[®]) on treatment (i.e. did not early discontinue treatment) are eligible and will be included in this trial if they fulfil all the inclusion and do not present any of the exclusion criteria.

Please refer to section [8.3.1](#) (Source Documents) for the documentation requirements pertaining to the in- and exclusion criteria.

3.3.2 Inclusion criteria

1. Male or female patients who completed the INBUILD[®] trial as planned and who did not prematurely discontinue blinded treatment.
2. Signed and dated written informed consent in accordance with ICH-GCP and local legislation prior to admission to the trial.
3. Women of childbearing potential (WOCBP)¹ must continue to use highly effective methods of birth control per ICH M3 (R2) that result in a low failure rate of less than 1% per year when used consistently and correctly, as well as one barrier method, for 28 days prior to and 3 months after nintedanib administration. A list of contraception methods meeting these criteria is provided in the patient information and in section [4.2.2.4](#).

3.3.3 Exclusion criteria

1. Any disease that may put the patient at risk when participating in this trial. Reconsider carefully all exclusion criteria of the INBUILD[®] trial (see Appendix [10.1](#)). However, patients may qualify for participation even though exclusion criteria may have been met during the course of participation in INBUILD[®], if the investigator's benefit-risk assessment remains favourable.
2. Patients who must or wish to continue the intake of restricted medications (see section [4.2.2.1](#)) or any drug considered likely to interfere with the safe conduct of the trial
3. Patient not compliant in parent trial (INBUILD[®]), with trial medication or trial visits, according to investigator's judgement.
4. Previous enrolment in this trial.

¹ A woman is considered of childbearing potential (WOCBP), i.e. fertile, following menarche and until becoming post-menopausal unless permanently sterile.

Permanent sterilisation methods include hysterectomy, bilateral salpingectomy and bilateral oophorectomy.

Tubal ligation is NOT a method of permanent sterilisation.

A postmenopausal state is defined as no menses for 12 months without an alternative medical cause.

Proprietary confidential information © 2020 Boehringer Ingelheim International GmbH or one or more of its affiliated companies

5. Chronic alcohol or drug abuse or any condition that, in the investigator's opinion, makes the patient an unreliable trial participant or unlikely to complete the trial.
6. Women who are pregnant, nursing, or who plan to become pregnant while in the trial.

3.3.4 Withdrawal of patients from treatment or assessments

Patients may discontinue trial treatment or withdraw consent to trial participation as a whole ("withdrawal of consent"); please see sections [3.3.4.1](#) and [3.3.4.2](#) below.

The decision to discontinue trial treatment or withdraw consent to trial participation and the reason must be documented in the patient files and CRF. If the reason for discontinuation is death, this should be reported on the SAE form as well, regardless of causal relationship. These data will be included in the trial database and will be reported.

3.3.4.1 Discontinuation of trial treatment

An individual patient will permanently discontinue trial treatment if:

- The patient experiences signs of hepatic injury, defined in section [5.2.5.1.4](#)
- In the opinion of the investigator, the patient experiences unacceptable adverse events despite dose adjustments and supportive care.
- The patient has repeatedly shown to be non-compliant with important trial procedures and, in the opinion of both, the investigator and sponsor representative, is not willing or able to adhere to the trial requirements in the future.
- The patient needs to take prohibited concomitant medication as defined in section [4.2.2](#) "Restrictions".
- The patient can no longer receive nintedanib for medical reasons
- Pregnancy: if a patient becomes pregnant during the trial, nintedanib needs to be stopped and the patient should be followed up until birth or otherwise termination of the pregnancy. The data of the patient will be collected and reported in the clinical trial report (CTR) until patient's last visit and any events thereafter will be reported in the BI drug safety database. Refer to section [5.2.5.2.4](#) for detailed information on event reporting in case of pregnancy.

In the following cases discontinuation of nintedanib is highly recommended. Only in special circumstances, the investigator, upon thorough assessment of all available clinical data and taking into consideration the potential risks associated with administration of nintedanib, may decide not to withdraw the trial medication, even though one or more of the below mentioned criteria are fulfilled. In such a case, continuation of treatment with trial medication should be discussed with the patient, and the decision and reasoning documented in the source data.

- Major surgery, including any abdominal or intestinal surgery.
- Anti-coagulation. Patients who require full-dose therapeutic anticoagulation (e.g. vitamin K antagonists, heparin, hirudin, direct thrombin inhibitors, factor Xa inhibitors etc.), or high-dose antiplatelet therapy. (Prophylactic low dose heparin or heparin flush as needed for maintenance of an indwelling intravenous device (e.g. enoxaparin 4000 I.U. s.c. per day), as well as prophylactic use of antiplatelet therapy (e.g. acetyl salicylic acid up to

Proprietary confidential information © 2020 Boehringer Ingelheim International GmbH or one or more of its affiliated companies

325 mg/day, or clopidogrel at 75 mg/day, or equivalent doses of other antiplatelet therapy is allowed.).

- Major thrombo-embolic events e.g. stroke, deep vein thrombosis, pulmonary embolism, myocardial infarction.

In case of a temporary interruption, trial treatment should be restarted if medically justified, please see section [4.2.1](#).

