4.2.1.2 Management of liver enzyme elevation

Evaluate the concomitant use of other drugs known to cause liver enzyme elevations. For a detailed guidance on how to manage liver enzyme elevations, please refer to Table 4.2.1.2: 1.

Table 4.2.1.2: 1 Management of liver enzyme elevations

AST or ALT increase to			Signs of hepatic injury* (section 5.2.5.1.4)	
>1.5x to <3x ULN	$\geq 3x$ to <5x ULN and no signs of hepatic injury (section 5.2.5.1.4)	$\geq 5x$ to <8x ULN and no signs of hepatic injury (section 5.2.5.1.4)		
Continue as planned ¹	Reduce dose or interrupt trial medication ²	Interrupt trial medication	Permanently discontinue / interrupt trial medication	
	Close observation ³ After 2 weeks or any time later	Close observation ³ After 2 weeks or any time later		CLINICAL EVALUATION OF HEPATIC-INJURY⁴ (section 5.2.5.1.4)
<3x ULN	$\geq 3x$ ULN	< 3x ULN	$\geq 3x$ ULN	
Reduced: return to initial dose. Interrupted: restart at reduced dose. Monitor every 2 weeks for at least 8 weeks	Permanently discontinue trial medication Close observation ³	Restart at reduced dose Monitor weekly for 4 weeks, then every 2 weeks for at least 8 weeks	Permanently discontinue trial medication. Close observation ³	

Footnotes:

*Signs of hepatic injury are defined as

- ALT and/or AST ≥ 8 fold ULN
- ALT and/or AST ≥ 3 fold ULN and total bilirubin ≥ 2 fold ULN
- ALT and/or AST ≥ 3 fold ULN and unexplained INR $> 1,5$
- ALT and/or AST ≥ 3 fold ULN and unexplained eosinophilia ($> 5\%$)
- ALT and/or AST ≥ 3 fold ULN and appearance of fatigue, nausea, vomiting, right upper abdominal quadrant pain or tenderness, fever and/or rash

¹ According to visit schedule. Consider additional control visits as adequate.

² To be decided by Investigator, based on individual risk assessment.

³ Close observation: Re-test ALT and AST, alkaline phosphatase, total bilirubin, and eosinophils within 48 to 72 hours, then after approximately 7 days and after approximately 2 weeks by using intermediate visit lab kit.

⁴ If clear evidence for alternative cause for hepatic injury was identified and resolved (i.e. relation to trial medication excluded, hepatic injury confirmed to have alternative explanation [other than use of IMP]): return to trial medication would be possible, after consultation with the sponsor. Prior to restart, liver laboratory values must be normal. Monitor weekly for first 4 weeks of re-introduction and every 2 weeks for the following 8 weeks.

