The laboratory tests at Visit 2, Visit 4, Visit 5a, Visit 6a and Visit 7a will include:

Table 5.2.3: 2

Laboratory tests at Visit 2, Visit 4, Visit 5a, Visit 6a and Visit 7a

Category	Laboratory test
Biochemistry	Total protein, creatinine, electrolytes (sodium, potassium, calcium, chloride, inorganic phosphorus) and liver function (AST, ALT, GGT, alkaline phosphatase, and total bilirubin)
Local Urine dipstick pregnancy test in all women of childbearing potential. If urine test is not acceptable to local authorities, a blood test must be done at a local laboratory.	

The laboratory samples taken at intermediate ‘a’ visits (Visits 5a, 6a and 7a) and any samples taken for additional safety monitoring (see section [4.2.1.2](#)) may be collected at the office of a local doctor using trial specific lab kits that will be sent to a central laboratory for analyses. These kits will be provided to patients at study visits as applicable.

Creatinine clearance will be calculated based on serum creatinine according to Cockcroft and Gault ([R96-0690](#)), Appendix [10.2](#)).

If laboratory values indicate abnormality, adequate and more frequent blood sampling may be performed at the discretion of the Investigator. Dependent on concomitant treatments, additional safety monitoring should be considered at the discretion of the investigator.

In case of liver function value elevations, close monitoring must be ensured by the Investigator. Refer to section [4.2.1.2](#) for monitoring elevations and section [3.3.4](#) for withdrawal criteria.

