6.2.2 Treatment period(s)

Subsequent clinic visits will be scheduled after 2, 4, 8, 12, 24, 36 and 48 weeks of treatment (Visits 2- 8). After the first 48 weeks of treatment (Visit 8), complete clinic visits will be scheduled every 12 weeks until at least Week 96 (Visit 12) and thereafter until the patient's end of trial.

Intermediate lab tests ('a' visits) will be performed if needed at 18, 30 and 42 weeks (Visits 5a, 6a and 7a) at the discretion of the investigator. The laboratory samples taken at these visits and any samples taken for additional safety monitoring (see sections [4.2.1.2](#) and [5.2.3](#)) may be collected at the office of a local doctor using trial specific lab kits that will be sent to a central laboratory for analyses. These kits will be provided to patients at study visits as applicable.

If possible, ECG should be performed prior to blood draw.

For detailed description of the trial procedures at each visit and dispensing schedule, please refer to [section 5](#) and the [Flowchart](#).

Dose Modification Visit

If the dose is reduced or increased (refer to section [4.1.3](#)) patients may need to come to the investigational site for a dose modification visit where the following will be performed:

- Physical examination including weight
- Vital signs

- Assessment of adverse events and concomitant therapy since last visit
- Assignment of new dose in IRT and trial medication dispensation
- Trial medication will be collected and drug accountability and treatment compliance will be reviewed

End of Treatment (EOT)

If a reason for drug discontinuation is met or when the trial is terminated due to one of the reasons mentioned in section [3.3.4](#), an End of Treatment Visit (EOT) should be scheduled as soon as possible after last drug intake for all patients. Reason for discontinuation must be documented in the eCRF. IRT should always be notified on end of treatment (EOT).

Adverse events that are ongoing at EOT should be followed up according to section [5.2.5.2.3](#).

For detailed description of the trial procedures at the EOT visit, please refer to the [Flowchart](#).

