6.2.3 Follow up period and trial completion

A follow-up (FU) visit must be conducted 28 days after last drug intake if trial medication was discontinued permanently due to adverse events. A FU visit does not need to be conducted for patients who stop for any other reason.

For detailed description of the trial procedures at the FU visit, please refer to the Flowchart.

If the reason for removal of a patient from the treatment is an adverse event, the patient must be followed until complete resolution or stabilization of the event for at least 28 days after the onset of the event or until follow-up is considered adequate by the investigator and clinical monitor.

A patient will be lost to follow-up if the investigator is not able to contact him/her despite multiple attempts. Every effort must be made; at least 2 telephone contacts plus 1 mailing should be documented. The site must notify the clinical monitor prior to designating a patient as lost to follow up.

For patients who permanently discontinue nintedanib due to adverse events, the FU Visit will be the trial completion visit. For all other patients the EOT visit will be the trial completion visit.

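### Signs of hepatic injury: Protocol 3.3.4.1 requires permanent discontinuation, Table 4.2.1.2:1 footnote 4 allows a conditional return, and SAP iPD C2(a) has no line for such a return

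*Protocol*

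**What the plan says.** **Protocol 3.3.4.1** has two lists. The first is mandatory ("An individual patient will permanently discontinue trial treatment if"), and its first entry reads "The patient experiences signs of hepatic injury, defined in section" 5.2.5.1.4. The second is discretionary ("In the following cases discontinuation of nintedanib is highly recommended") and covers major surgery, anticoagulation or high-dose antiplatelet therapy, and major thrombo-embolic events. The section closes with a sentence on restarting after a temporary interruption, which refers to 4.2.1.

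**Protocol Table 4.2.1.2:1** gives the action for the same signs as "Permanently discontinue / interrupt trial medication". Under footnote 4, if an alternative cause is clearly shown and has resolved, "return to trial medication would be possible, after consultation with the sponsor. Prior to restart, liver laboratory values must be normal".

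**Protocol 5.2.5.1.4** requires an immediate stop and follow-up by the DILI checklist. It does not say whether the stop is permanent.

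**Protocol 1.4** says two things. For hepatic toxicity the drug is to be reduced or interrupted and then held until the laboratory values recover (citing 4.2.1.2 and 5.2.5.1.4). For severe liver enzyme elevations as specified in 3.3.4, it must be discontinued.

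**SAP Table 6.2:1, C2(a)** describes the deviation as drug not permanently discontinued after signs of hepatic injury, as defined in CTP 5.2.5.1.4 and 4.2.1.2. Its Requirements column instead covers subjects whose liver signs were not handled as the CTP requires. It is determined manually, and nobody is excluded for it.

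**The concern.** Two operative sections of the current protocol answer one question differently: may a patient who has met the hepatic injury criteria ever resume trial drug? Under the first list of 3.3.4.1 the answer is no. Under footnote 4 it is yes, on conditions.

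Hepatic injury is one of only two adverse events of special interest in this trial, and re-exposure after it is the step on which the two rules differ. Both rules take the patient off drug at the alert, so the immediate response is not in dispute.

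The two answers also lead to different visit paths and different entries in the exposure and deviation tables. Sites acting in good faith, and a reviewer classifying their cases, could therefore treat identical cases differently.

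**Working it through.** No arithmetic applies. The trial is descriptive, and the documents give no rate from which to count affected patients. The check sets the passages side by side and then traces one case.

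**Step 1: the protocol wording**

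| Place | Trigger | Action | Return to drug |
|---|---|---|---|
| 3.3.4.1, first list | Signs per 5.2.5.1.4 | Permanent discontinuation | None stated |
| 3.3.4.1, closing sentence | Any temporary interruption; liver not named | Restart if justified, see 4.2.1 | General only |
| Table 4.2.1.2:1 | Same signs | Permanent discontinuation or interruption | Conditional, footnote 4 |
| 5.2.5.1.4 | Same signs | Immediate stop | Silent |
| 1.4, liver paragraph | Hepatic toxicity | Reduce or interrupt, hold until recovery | Implied |
| 1.4, monitoring paragraph | Severe liver enzyme elevations, per 3.3.4 | Discontinue | None stated |

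**Step 2: does anything rank these?** No section does. Section 5.2.3 sends the reader to 4.2.1.2 for monitoring and to 3.3.4 "for withdrawal criteria", which leads back to the rule without an exception. The investigator's discretion in 3.3.4.1 covers only the second list, and hepatic injury is not in it.

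**Step 3: one case through the protocol.** A patient shows signs of hepatic injury. An alternative cause is confirmed and resolves, the sponsor is consulted, liver values are normal, and the drug is resumed.

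- *Under 3.3.4.1:* the resumption is barred. Section 6.2.2 ("If a reason for drug discontinuation is met") calls for an EOT visit as soon as possible after last intake, and 6.2.3 adds: "For patients who permanently discontinue nintedanib due to adverse events, the FU Visit will be the trial completion visit".
- *Under footnote 4:* the resumption is allowed, which presupposes that the patient is still in the trial and that the stop was an interruption.

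**Step 4: the same case through SAP C2(a)**

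| Reading | Result |
|---|---|
| Description column | Deviation (not permanently discontinued) |
| Requirements column, applied with 3.3.4.1 | Deviation |
| Requirements column, applied with footnote 4 | No deviation (protocol followed) |

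C2(a) cites 4.2.1.2 only for how hepatic injury is defined, so the citation does not bring in footnote 4's action rule.

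**Step 5: what moves in the analysis.** The site's choice decides whether the case is summarised as a premature discontinuation or an interruption (SAP 5.4.3.1.1 and 7.7). Because time at risk for a patient without a given event can run to 28 days after last intake (SAP 7.8.1.1), that patient's observation time can also change. The Treated Set is fixed by the first dose (SAP 6.3), the primary endpoint definition is untouched, and the patient already counts in the hepatic injury proportion (SAP 5.4.4) once the signs occur.

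**The case against.** The strongest reply is that 3.3.4.1 does contain a route back. Its last sentence provides for restart after a temporary interruption and points to 4.2.1, the parent of the section that holds footnote 4. A reader might infer that 3.3.4.1 has no restart provision at all, and that would be wrong. But the sentence does not name hepatic injury, and it applies only once a stop is classed as temporary, which the first list says this one is not. It narrows the conflict without resolving it.

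Second, footnote 4 requires sponsor consultation, so a site following it cannot re-expose a patient without that case being raised. This stands, and it limits how far practice could drift. It does not tell the site which section governs.

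Third, a reader might infer that C2(a) is unworkable. The documents do not support that. C2 is a manual determination, handled under a sponsor standard that is not among the documents, and a reviewer can decide each case. What is missing is a pre-specified line for a footnote 4 return.

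Fourth, the visit-path difference follows from the same conflict; it is not a second error. The timing of the follow-up visit does not measure the size of the problem, and neither does the number of deviation codes affected.

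**Conclusion.** The inconsistency is real and lies in the current text; it does not depend on the amendment history. It is worth correcting because it concerns re-exposure after an adverse event of special interest.

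Its reach is narrow. It affects only patients who show signs of hepatic injury and then meet every footnote 4 condition. That number cannot be derived from the documents and is likely small. It would be tempting to conclude that the primary result or an analysis population is compromised. The documents do not support that: there is no per-protocol set, C2 excludes nobody, and the Treated Set and the primary endpoint definition stay as they are. The possible differences are re-exposure, handling as discontinuation or interruption, and the reported deviation count.

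The conclusion assumes that neither the DILI checklist nor the sponsor's deviation standard, which the documents cite but do not reproduce, settles precedence. It takes no position on which clinical rule is right.

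**What to change.** **Protocol.** Reconcile Section 1.4 (both statements), Section 3.3.4.1 (the hepatic entry and the closing sentence), Table 4.2.1.2:1 with footnote 4, and Section 5.2.5.1.4 to a single rule. The choice of rule is the sponsor's, and none is proposed here. Aligning only 3.3.4.1 and the table would leave 1.4 and 5.2.5.1.4 unaligned. State also whether the EOT and follow-up path of 6.2.2 and 6.2.3 starts at the alert.

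**SAP.** Align both columns of C2(a) with the result and add one line: *A return to trial medication under footnote 4 of CTP Table 4.2.1.2:1 [is / is not] counted under C2(a).*

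**Editorial only.** The asterisk footnote of Table 4.2.1.2:1 omits the same-blood-draw condition that 5.2.5.1.4 and SAP 5.4.4 carry. It could add the condition or simply cite 5.2.5.1.4.

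**Cost.** The protocol change is a wording amendment, which under Section 8.1 needs ethics and competent-authority approval, in about 15 countries. The SAP change is one table row. Neither needs new data or alters an analysis set. The SAP line is useful on its own even if patients have finished treatment, because it makes the deviation count reproducible.
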